## 5.2 Contraception Recommendations

---

### Contraception Requirements for Females

Subjects must follow the following contraceptive guidelines as specified:

#### Females, Non-Childbearing Potential

Females do not need to use birth control during or following study drug treatment if considered of non-childbearing potential due to meeting any of the following criteria:

1. Premenopausal female with permanent sterility or permanent infertility due to one of the following:
  - Permanent sterility due to a hysterectomy, bilateral salpingectomy, bilateral oophorectomy.
  - Non-surgical permanent infertility due to Mullerian agenesis, androgen insensitivity, or gonadal dysgenesis; investigator discretion should be applied to determining study entry for these individuals.
2. Postmenopausal female
  - Age > 55 years with no menses for 12 or more months without an alternative medical cause.
  - Age ≤ 55 years with no menses for 12 or more months without an alternative medical cause AND a follicle-stimulating hormone (FSH) level ≥ 30 IU/L.

#### Females of Childbearing Potential

Review and document pregnancy avoidance recommendations with females of childbearing potential.

Females of childbearing potential must avoid pregnancy while taking study drug and for at least 30 days after the last dose of study drug. Females must commit to one of the following methods of highly effective birth control:

- Combined (estrogen- and progestogen-containing) hormonal birth control (oral, intravaginal, transdermal, injectable) associated with inhibition of ovulation initiated at least 30 days prior to study Baseline Day 1.
- Progestogen-only hormonal birth control (oral, injectable, implantable) associated with inhibition of ovulation initiated at least 30 days prior to study Baseline Day 1.
- Bilateral tubal occlusion/ligation (can be via hysteroscopy, provided a hysterosalpingogram confirms success of the procedure) (For Japan: only bilateral tubal ligation).
- Intrauterine device (IUD).
- Intrauterine hormone-releasing system (IUS).
- Vasectomized sexual partner (the partner has received medical confirmation of the surgical success of the vasectomy and is the sole sexual partner of the trial subject).
- Practice true abstinence (unless not acceptable per local practices), defined as: refraining from heterosexual intercourse when this is in line with the preferred and usual lifestyle of the subject (periodic abstinence [e.g., calendar, ovulation, symptothermal, post-ovulation methods] and withdrawal are not acceptable).

If required per local practices, females of childbearing potential must commit to using 2 methods of contraception (either 2 highly effective methods or 1 highly effective method combined with 1 effective method). Effective methods of birth control are the following:

- Progestogen-only oral hormonal contraception, where inhibition of ovulation is not the primary mode of action, initiated at least 30 days prior to Baseline Day 1.
- Male or female condom with or without spermicide.
- Cap, diaphragm, or sponge with spermicide.
- A combination of male condom with a cap, diaphragm, or sponge with spermicide (double barrier method).

Contraception recommendations related to use of concomitant therapies prescribed per standard of care should be based on the local label.

## 5.3 Prohibited Medications and Therapy

---

### Corticosteroids

Systemic corticosteroids for treatment of vitiligo including, but not limited to, oral, intravenous, IM, and intralesional are prohibited throughout the study. For non-vitiligo reasons, use of systemic corticosteroids can be used but limited to prednisone or prednisolone for up to 1 mg/kg/day for no more than 2 consecutive weeks; any subject who receives systemic corticosteroids for more than 2 consecutive weeks, regardless of the dosage of corticosteroid, should permanently discontinue study drug.

## Topical Therapy

Topical treatments for vitiligo (including, but not limited to topical calcineurin inhibitors, topical corticosteroids, topical prostaglandin analogs) are prohibited until after Week 24 Visit assessments. Subjects are not permitted to receive permanent or temporary tattoos within 30 days prior to the first dose of study drug through the end of the study.

## Phototherapy, Tanning Booth, Extended Sun Exposure, and Surgical Grafting

Phototherapy (including, but not limited to, broadband UV-B, narrowband UV-B, psoralen and UV-A, excimer or other laser therapy, tanning booth use) is prohibited for at least 12 weeks prior to the Baseline Visit and prohibited during the study. However, subjects are allowed to receive natural daily light following a normal routine, but, for a prolonged exposure to sunlight, sunscreen is recommended. Surgical grafting for vitiligo is not allowed during the study.

## Supplemental Vitiligo Therapy Including Over the Counter (Antioxidants/Vitamins/Herbal Medicine/Traditional Chinese Medicine)

Supplemental therapy for vitiligo (including, but not limited to, antioxidants, vitamins, herbal supplements, traditional Chinese medicine) is not permitted until after Week 24 Visit assessments. However, for any drugs that are considered strong CYP3A inhibitors or inducers, or any herbal supplements or traditional medicines with unknown effects on CYP3A are prohibited throughout the entire the study. Subjects must have discontinued supplemental therapies at least 30 days prior to the first dose of study drug.

## JAK Inhibitors

Prior and concomitant oral and topical exposure to any other JAK inhibitors besides the investigational drug, upadacitinib, in this study (including but not limited to ruxolitinib [Jakafi®], tofacitinib [Xeljanz®], baricitinib [Olumiant®], abrocitinib [PF-04965842], and filgotinib) is not allowed.

## Targeted Biologic Therapies

Subjects must have discontinued immunomodulatory biologic therapies prior to the first dose of study drug as specified in the washout procedures (Eligibility Criterion 19, Protocol Section [5.1](#)). No minimum washout prior to Baseline is required for a biologic therapy if an undetectable drug level measured by a commercially available assay is documented.

Current and concomitant biologic therapies and biosimilar versions of biologic drugs are prohibited during the study. Examples of biologic therapies include, but are not limited to, the following:

- Humira® (adalimumab)
- Dupixent® (dupilumab)
- Zolair® (omalizumab)
- Enbrel® (etanercept)
- Remicade® (infliximab)
- Orencia® (abatacept)

- Kineret® (anakinra)
- Rituxan® (rituximab)
- Cimzia® (certolizumab pegol)
- Simponi® (golimumab)
- Actemra® (tocilizumab)
- Raptiva® (efalizumab)
- Tysabri® (natalizumab)
- Stelara® (ustekinumab)
- Benlysta® (belimumab)
- Taltz® (ixekizumab)
- Cosentyx® (secukinumab)
- Tremfya® (guselkumab)
- SKYRIZI® (risankizumab) or SKYRIZI® (risankizumab-rzaa)

### Other Non-Biologic Systemic Therapy

Other systemic therapy for the treatment of vitiligo is prohibited during the study including, but not limited to:

- MTX
- cyclosporine
- azathioprine
- phosphodiesterase type 4 -inhibitors (e.g., apremilast)
- mycophenolate mofetil

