Key Eligibility Criteria:	
Eligible subjects will be adult females and males ≥ 18 to 65 years of age at Screening with a clinical diagnosis of NSV and no segmental or localized vitiligo, with all of the following at Screening and Baseline Visits: ≥ 0.5 F-VASI and ≥ 5 total Vitiligo Area Scoring Index (T-VASI). Subjects with other skin conditions that would interfere with evaluation of vitiligo, subjects with uncontrolled thyroid disease, and subjects with > 33% leukotrichia on the face or > 33% leukotrichia on the body (including face) are not eligible to enroll in this study.
 
Eligible subjects must not have previously been treated with any topical or systemic JAK inhibitor. Also, subjects must not have been previously treated with any permanent skin bleaching agents to treat vitiligo. Subjects must not have been treated with any systemic vitiligo therapy (e.g., methotrexate, mycophenolate mofetil, corticosteroids), supplemental vitiligo therapy (antioxidants/vitamins/herbal medicine/traditional Chinese medicine), and/or topical vitiligo therapy including permanent or temporary tattoos within a minimum of 30 days prior to the first dose of study drug (Note: Camouflage and makeup may be used). Eligible subjects must not have been treated with any phototherapy, including excimer (or other forms of laser therapy), within a minimum of 12 weeks prior to the first dose of study drug. Subjects who have had prior exposure to immunomodulatory

	
biologic therapy, for any indications, must have discontinued the biologic therapy prior to the first dose of study drug. Recommended washout periods for biologic therapies include <math>\geq 4</math> weeks for etanercept; <math>\geq 8</math> weeks for adalimumab, infliximab, certolizumab, golimumab, abatacept, tocilizumab, and ixekizumab; <math>\geq 16</math> weeks for secukinumab; and <math>\geq 12</math> weeks for ustekinumab. For biologic therapies not specified, therapies must be discontinued at least 5 times the mean terminal elimination half-life of a drug or 3 months prior to Baseline, whichever is longer.

Study Drug and Duration of Treatment:	
Upadacitinib 6 mg QD extended-release, film-coated tablets for oral administration, 52 weeks in duration.  Upadacitinib 11 mg or 22 mg QD extended-release, film-coated tablets for oral administration, 28 or 52 weeks in duration.  Placebo for upadacitinib QD film-coated tablets for oral administration, 24 weeks in duration.

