  - Hepatitis C virus (HCV): detectable HCV RNA in any subject with anti-HCV Ab.
- ✓ 11. Subjects must not have any of the following medical diseases or disorders:
  - Recent (within past 6 months) cerebrovascular accident, myocardial infarction, coronary stenting, and aorto-coronary bypass surgery;
  - History of an organ transplant which requires continued immunosuppression;
  - History of GI perforation (other than due to appendicitis or mechanical injury), diverticulitis, or significantly increased risk for GI perforation per investigator judgment;
  - Conditions that could interfere with drug absorption including but not limited to short bowel syndrome or gastric bypass surgery; subjects with a history of gastric banding/segmentation are not excluded;
  - History of malignancy except for successfully treated NMSC or localized carcinoma in situ of the cervix;
  - Uncontrolled thyroid disease;
  - Other skin conditions that would interfere with evaluation of vitiligo;
  - > 33% leukotrichia on the face or > 33% leukotrichia on the body (including face).
- ✓ 12. There must be no reason the investigator believes that the subject is an unsuitable candidate to participate in the study, receive study drug, or would be placed at risk by participating in the study.

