#### Prior and Concomitant Medications and Therapies

- ✓ 16. Subjects must not have previously been treated with any topical or systemic JAK inhibitor.
- ✓ 17. Subjects must not have previously been treated with any permanent skin bleaching agents to treat vitiligo.
- ✓ 18. Subjects must not have been treated with any investigational drug of chemical or biologic nature within a minimum of 30 days or 5 half-lives (whichever is longer) prior to the first dose of study drug or is currently enrolled in another interventional clinical study or was previously enrolled in this study.
- ✓ 19. Subjects who have had prior exposure to immunomodulatory biologic therapy, for any indications, must have discontinued the biologic therapy prior to the first dose of study drug. Recommended washout periods are specified below. If not specified below, biologic therapies must be discontinued at least 5 times the mean terminal elimination half-life of a drug or 3 months prior to Baseline, whichever is longer.
  - $\geq 4$  weeks for etanercept;
  - $\geq 8$  weeks for adalimumab, infliximab, certolizumab, golimumab, abatacept, tocilizumab, and ixekizumab;
  - $\geq 16$  weeks for secukinumab;
  - $\geq 12$  weeks for ustekinumab.
- ✓ 20. Subjects must not have been treated with any systemic vitiligo therapy (e.g., methotrexate [MTX], mycophenolate mofetil, corticosteroids) or supplemental vitiligo therapy (antioxidants/vitamins/herbal medicine/traditional Chinese medicine) within a minimum of 30 days prior to the first dose of study drug.
- ✓ 21. Subjects must not have been treated with any topical vitiligo therapy including permanent and temporary tattoos within a minimum of 30 days prior to the first dose of study drug. (Note: Camouflage and makeup may be used).
- ✓ 22. Subjects must not have been treated with any phototherapy, including excimer (or other forms of laser therapy), within a minimum of 12 weeks prior to the first dose of study drug.

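### Methotrexate, cyclosporine, azathioprine, PDE4 inhibitors and mycophenolate are barred only as vitiligo treatment, so their use for another disease has no drug-specific entry or on-study rule

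*Protocol*

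**What the plan says.** **The class in question.** Under Other Non-Biologic Systemic Therapy, Protocol Section 5.3 reads "Other systemic therapy for the treatment of vitiligo is prohibited during the study including, but not limited to", followed by five entries: methotrexate, cyclosporine, azathioprine, PDE4 inhibitors (apremilast as the example) and mycophenolate mofetil. The washout has the same limit. Criterion 20 begins "Subjects must not have been treated with any systemic vitiligo therapy (e.g., methotrexate [MTX], mycophenolate mofetil, corticosteroids" and sets 30 days before first dose. The Synopsis repeats it: "Subjects must not have been treated with any systemic vitiligo therapy (e.g., methotrexate, mycophenolate mofetil, corticosteroids".

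**The neighbouring classes.**
- JAK inhibitors: "Prior and concomitant oral and topical exposure to any other JAK inhibitors besides the investigational drug, upadacitinib, in this study" is not allowed, with no reference to indication.
- Biologics: "Current and concomitant biologic therapies and biosimilar versions of biologic drugs are prohibited during the study". At entry, criterion 19 states "Subjects who have had prior exposure to immunomodulatory biologic therapy, for any indications, must have discontinued the biologic therapy" before first dose.
- Systemic corticosteroids: banned for vitiligo. For other reasons, only prednisone or prednisolone up to 1 mg/kg/day is allowed, for at most 2 consecutive weeks, and "any subject who receives systemic corticosteroids for more than 2 consecutive weeks, regardless of the dosage of corticosteroid, should permanently discontinue study drug".

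**The concern.** The protocol separates vitiligo use from other use when it intends to: the steroid paragraph handles the two in turn, and criterion 19 names every indication. The non-biologic systemic paragraph carries the vitiligo qualifier with no companion rule for other uses. Taken literally, methotrexate for rheumatoid arthritis or azathioprine for inflammatory bowel disease is permitted at entry and throughout the 24 + 28 = 52 weeks. More than two consecutive weeks of prednisone at any dose ends study drug; a year of cyclosporine for another disease does not.

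The situation is foreseeable. Protocol Section 2.1 names psoriasis, rheumatoid arthritis, lupus and inflammatory bowel disease among the conditions associated with vitiligo.

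Safety is part of the primary objective. Section 2.2 reports raised infection risk and falls in white cells with upadacitinib, and Section 6.1 makes serious infection, neutropenia and lymphopenia events of special interest. In a dose-ranging trial, a second immunosuppressant makes it harder to attribute such an event to dose. The wording can also be read two ways, so practice may differ across about 35 sites.

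**Working it through.** **1. Does another rule close the gap?** Each candidate was set against the case of a subject taking one of the five drugs for a disease other than vitiligo.

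| Provision | What it does for this subject |
|---|---|
| Criterion 1; Section 5.9 | Enforce protocol requirements; here there is none to breach |
| Criterion 11 | Names "History of an organ transplant which requires continued immunosuppression" only |
| Criteria 7 and 12 | Investigator judgment on health and suitability |
| Section 5.3, CYP3A rule | Applies whatever the indication, but Table 1 names none of the five drugs among its examples |
| Section 5.4 | Records drug, reason, dates and dose; restricts nothing |
| Section 5.5, medication stop rule | Covers prohibited medication, and only when continuing is a risk |
| Section 5.5, general stop rules | Investigator or medical-director discretion |
| Section 6.2 | Interrupts study drug after an infection or laboratory abnormality |
| SAP Section 8.0 | Names treatment discontinuation as the only intercurrent event |
| SAP 10.5; Appendix A | No safety subgroups; counts only prohibited medication as a deviation |

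None is a drug-specific entry or on-study rule. The operations manual is not among the documents and could not be checked.

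**2. Efficacy scale.** Inputs from Protocol Section 7.8: 40 per arm, difference 40 points, SD 54.8, two-sided alpha 0.1, two-sample t-test.

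The plan's own figure first. SE of the difference = 54.8 × √(2/40) = 12.25. Noncentrality = 40 / 12.25 = 3.26, with 78 df. Power for one dose against placebo = 94.4% (normal approximation 94.7%), which agrees with the stated figure of more than 90%.

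Assumption, not from the documents: k of 40 subjects in each arm take such a drug, upadacitinib adds nothing in them, and the SD is unchanged. Difference = 40 × (1 − k/40).

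| k of 40 | Difference (points) | Power per dose |
|---|---|---|
| 0 | 40 | 94.4% |
| 1 | 39 | 93.4% |
| 2 | 38 | 92.4% |
| 4 | 36 | 89.7% |

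The largest shift shown, 4 points, is 4 / 12.25 = 0.33 SE.

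**3. Safety scale.** With full exposure, a 40-subject arm in Period 1 has 40 × 168 / 365.25 = 18.4 patient-years. One event is 100 / 18.4 = 5.4 per 100 patient-years, or 1/40 = 2.5% of subjects. In the ALL_UPA set, the 22 mg group has at most (40 × 364 + 20 × 196) / 365.25 = 50.6 patient-years, so one event is about 2.0 per 100. These figures hold for any single event in a group of that size. They show how far one event of uncertain cause can move a dose-specific rate; they do not measure the gap itself.

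**The case against.** The other side has real weight.

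- **General stop rules exist.** Section 5.5 requires study drug to stop when the investigator judges it best for the subject, or when events or laboratory results rule out safe continuation. The sponsor's medical director may also mandate a stop. A reader might infer that nothing could end the combination; the documents do not support that.
- **The harms are monitored.** Section 6.2 interrupts dosing for serious infection and at set hemoglobin, neutrophil, lymphocyte and white-cell thresholds. The data monitoring committee sees unblinded safety data about every 4 months.
- **Use would be visible.** SAP 7.0 and 7.3 tabulate concomitant medication by generic name and treatment group, SAP 10.2.5 lists events of special interest, and Section 5.4 captures the reason for use. Individual cases can be examined.
- **The exposed group is narrow.** Criterion 11 removes transplant immunosuppression and skin disease that would hinder vitiligo assessment, which would take out some psoriasis. Protocol Section 4.2 expects little background treatment.
- **The contrast with steroids is partial.** A reader might infer that every neighbouring class has a washout, a cap and a stop rule that this one lacks. That goes too far. Steroids for non-vitiligo reasons have a cap and a stop rule but no washout, because criterion 20 limits theirs to vitiligo too. JAK inhibitors have an outright bar.

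All of this stands, and it lowers the severity. It does not close the gap: these provisions are discretionary, act after an event or record what happened. None keeps the combination from starting or continuing. A site might read the drug list as a full ban, but the text does not say so.

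**Conclusion.** The concern holds as a gap in the rules on concomitant treatment: the five named entries are restricted only as vitiligo therapy, while each neighbouring immunomodulator class has at least one rule that applies whatever the indication. It is worth correcting but is not a threat to the trial's main result.

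The consequence is mainly for safety and for attributing infections and cytopenias to dose. Because the protocol itself treats these drugs as vitiligo therapy, a reader might infer biased efficacy. The documents do not support that: randomization balances use on average, leaving dilution or chance imbalance, and the power loss is 1 to 2 points for 1 or 2 users per arm and under 5 points for 4 of 40.

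This rests on a literal reading of the protocol without the operations manual, and on assumed usage rates. The documents give no frequency, and Section 4.2 suggests that it is low.

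**What to change.** 1. **Section 5.3.** Add a sentence prohibiting methotrexate, cyclosporine, azathioprine, PDE4 inhibitors and mycophenolate mofetil during the study for any indication. Keep the existing open-ended ban for vitiligo therapy only. Simply replacing the vitiligo qualifier with any indication would, on an open list, bar all systemic therapy.
2. **Criterion 20 and Synopsis.** Add a separate sentence requiring a 30-day washout of those named drugs for any indication. Leave the steroid and supplement wording unchanged.
3. **Subjects already enrolled on such a drug.** Require a case-by-case safety review with the sponsor's medical director, and flag them in the adverse event and special-interest listings.

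Cost: one protocol amendment touching three places, plus the listing flag. No new data collection is needed, because Section 5.4 already records reason, dates and dose. The downside is that a few subjects with a treated autoimmune comorbidity are excluded, which narrows the population slightly.

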### Investigational Drugs

Subjects who have been treated with any investigational drug within 30 days or 5 half-lives of the drug (whichever is longer) prior to the first dose of study drug are excluded from participation in this study. Investigational drugs are also prohibited during the study.

### Vaccines

Live vaccines are prohibited during study participation and including at least 30 days (or longer if required locally) after the last dose of study drug. If the subject and investigator choose to receive/administer live vaccines, these vaccinations must be completed at least 28 days (or longer if required locally) before first dose of study drug with appropriate precautions. Although not mandated by the protocol, vaccines recommended by local guidelines should be considered. Examples of live vaccines include, but are not limited to, the following:

- Monovalent live attenuated influenza A (H1N1) (intranasal)
- Seasonal trivalent live attenuated influenza (intranasal)
- Zostavax (herpes zoster, live attenuated)
- Rotavirus
- Varicella (chicken pox)
- Measles-mumps-rubella or measles-mumps-rubella-varicella
- Oral polio vaccine
- Smallpox
- Yellow fever
- Bacille Calmette-Guérin
- Typhoid (oral)

Administration of inactivated (non-live) vaccines is permitted prior to or during the study according to local practice guidelines. Examples of common vaccines that are inactivated, toxoid, or biosynthetic include, but are not limited to, injectable influenza vaccine, pneumococcal, Shingrix (zoster vaccine, recombinant, adjuvanted), and pertussis (Tdap) vaccines.

### **COVID-19 Vaccine**

Whenever possible, subjects should not have received a COVID-19 vaccination in the 7 days prior to randomization or plan to receive a COVID-19 vaccination within the first 7 days after initiation of study drug.

